6.5.2 VECTOR ANALYSES

Vector analysis will be conducted in accordance with Eydelman 2006³ for eyes with astigmatism (magnitude of preoperative MRC >0.50 D).

Vector Stability of MRC

Vector stability of MRC will be evaluated for two cohorts: a "consecutive cohort" (eyes with data at two consecutive visits) and a "consistent cohort" (eyes with data at all periodic visits through the point of stability and the confirmatory time point).

The frequency, proportion and 95% confidence intervals of eyes with vector MRC change \leq 1.00 D, as well as \leq 0.50 D, between visits will be reported. Mean, standard deviation and 95% confidence

³ Eydelman M, Drum B, Holladay J etc (2006). Standardized analyses of correction of astigmatism by Laser systems that reshape the cornea. Journal of Refractive Surgery 22: 81-95.

intervals of the mean magnitude of MRC vector change between visits and the mean MRC vector change per year and mean MRC vector change per month will be calculated and reported.

Vector Analysis Summary at Stability Time Point

The mean and standard deviation of intended refractive change (|IRC|), surgically induced refractive change (|SIRC|), error vector (|EV|), correction ratio (CR) and error ratio (ER) will be presented by preoperative MRC categories (>0.50 D to ≤1.00 D, >1.00 D to ≤ to 2.00 D, >2.00 D to ≤ to 3.00 D, >3.00 D to ≤ 4.00 D).

Error of Magnitude (EM) at Stability Time Point

The mean and standard deviation of EM will be presented by preoperative MRC categories (>0.50 D to ≤ 1.00 D, >1.00 D to ≤ 2.00 D, >2.00 D to ≤ 3.00 D, >3.00 D to ≤ 4.00 D). The frequency and proportion of eyes for each preoperative MRC category will be reported.

Error of Angle (EA) at Stability Time Point

The mean and standard deviation of EA will be presented by preoperative MRC categories (>0.50 D to ≤ 1.00 D, >1.00 D to ≤ 2.00 D, >2.00 D to ≤ 3.00 D, >3.00 D to ≤ 4.00 D). The frequency and proportion of eyes for with $|EA| \leq 15^{\circ}$, EA>+15° and EA $\leq 15^{\circ}$ will also be reported.

6.6 KERATOMETRIC ANALYSIS

Summary statistics (mean, standard deviation, median, minimum and maximum) will be reported over time for the Average Keratometry (AVK). Stability of average keratometry will be evaluated for two cohorts: a "consecutive cohort" (eyes with data at two consecutive visits) and a "consistent cohort" (eyes with data at all periodic visits through the point of stability and the confirmatory time point). The frequency, proportion and 95% confidence intervals of eyes with AVK changes ≤ 1.00 D, as well as ≤ 0.50 D, between visits will be presented.

The following formulas will be used:

- Average Keratometry (AVK) = (Flat + Steep) / 2
- |current AVK previous AVK $| \le 0.5$ and ≤ 1.00 D.

Additionally, summary statistics (mean, standard deviation, minimum and maximum) of mean keratometric cylinder magnitude (Kmax – Kmin) differences from preoperative to the stability time point will be presented. The absolute keratometric steep meridian axis shift (<15° and ≥15°) between preoperative and the stability time point stratified by keratometric cylinder magnitude (0.00 D, >0 D to ≤0.50 D, >0.50 D to ≤1.00 D, >1.00 D to ≤1.50D etc.) at the stability time point will also be reported. A listing of eyes with absolute keratometric axis shift ≥15° from preoperative to the stability time point will be provided.

6.7 HIGHER ORDER ABERRATIONS (HOA)

Analyses of higher order aberrations (HOA) from iDesign aberrometry measurements will include root mean square (RMS) values for total higher order aberrations and key specific components: coma, trefoil, and spherical aberration. Analyses will be performed for 5 mm wavefront diameters. HOA summary statistics (mean and standard deviation) will be reported over time.

A paired analysis will be done for HOA change between preoperative visit and at the stability time point. Mean change and 95% confidence interval will be provided for each HOA.

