#### 6.2 OTHER ENDPOINTS:

- 1. Monocular mesopic distance corrected contrast sensitivity with and without glare at spatial frequencies of 1.5, 3, 6, and 12 cpd
- 2. Monocular photopic distance corrected contrast sensitivity without glare at spatial frequencies 3, 6, 12 and 18 cpd
- 3. Binocular UCVA
- Manifest cylinder analyses (vector and non-vector)
- 5. iDesign aberrometry measurements (including higher order aberrations)
- 6. Keratometry (iDesign and auto/manual)
- 7. Intraocular pressure via applanation tonometry

17NOV2015/ 3.0 9 PR/STAR-115-MIPS

- 8. Anterior segment evaluation (biomicroscopic slit-lamp exam) for determination of medical findings including re-epithelialization, corneal clarity, complications, etc.
- 9. Visual symptoms via the patient reported outcomes (PRO) instrument Patient Reported Visual Symptom Questionnaire (PRVSQ for PRK/LASIK)
- 10. Ocular/visual symptoms (from non-directed responses obtained from the open-ended question "are you having any difficulties with your eyes or vision?")
- 11. National Eye Institute Refractive Error Quality of Life 42 (NEI-RQL) questionnaire results for all 13 sub-scales: dependence on correction, satisfaction with correction, activity limitations, far vision, clarity of vision, expectations, near vision, diurnal fluctuations, glare, symptoms, worry, suboptimal correction, and appearance
- 12. Ocular Surface Disease Index (OSDI) questionnaire
- 13. Schirmer I Tear Test (with anesthetic)
- 14. Exploratory satisfaction questionnaires non-validated questionnaires designed to collect patient satisfaction data prior to and following refractive corneal surgery

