#### 20.3 ADDITIONAL ENDPOINTS

Results for mesopic contrast sensitivity with and without glare (1.5, 3, 6, and 12 cpd) and photopic contrast sensitivity without glare (3, 6, 12, and 18 cpd) will be reported using nonparametric analyses. The frequencies and proportions of eyes with each acuity line changes of binocular UCVA will be reported over time. Mean MRSE, MRS and MRC outcomes, as well as the accuracy of MRS and MRC, will be presented over time. MRC will be analyzed using both non-vector and vector methods. Keratometric analyses will include mean average keratometry, stability of average keratometry, and keratometric cylinder analyses. Mean iDesign aberrometry measurements (HOA) and changes in HOAs will be presented. The mean change in Schirmer I Tear Test (with anesthetic) measurements will be evaluated. The change in intraocular pressure over time will also be evaluated. The frequency and proportion of biomicroscopic slit-lamp findings, including corneal clarity, will be reported over time. The frequency and proportion of eyes with spontaneously reported ocular visual symptoms (non-directed) as well as analyses of the PRVSQ for PRK/LASIK PRO for subjective visual symptoms will be presented. All 13 sub-scales of the NEI-RQL will be analyzed and reported over time. Additionally, mean scores for the OSDI PRO will be analyzed and reported over time. The frequency and proportion of patient satisfaction about the study procedure from the non-validated questionnaires designed to collect patient satisfaction data prior to and following refractive corneal surgery will be summarized. The numbers and proportions of eyes with complications and adverse events and retreatment procedures will be summarized.

Results from the PRSVQ questionnaires completed following the 3-month study visit will be used for reliability validation purposes for the PRSVQ only and will not be analyzed in this study or used for AE reporting.

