Nonvector – MRC accuracy (n, %, 95% CI of eyes wthin±0.5D and within±1.0D; mean and SD of attempted and achieved correction; % achieved) Nonvector – reduction of absolute cylinder (N, mean, min, max by preop MRC categories)
within±1.0D; mean and SD of attempted and achieved correction; % achieved) Nonvector – reduction of absolute cylinder (N, mean, min, max by preop MRC categories)
preop MRC categories)
Nonvector – absolute shift in axis (n and % of eyes with axis shift
by residual cylinder magnitude categories)
Vector- MRC stability– two sets of tables (consecutive/consistent cohorts) MRC vector change between visits (n, %, 95% CI of eyes of within ±0.5D /±1.0D change), mean rate of vector change per year, SD and the 95% CI, mean rate of vector change per year divided by 12 to get the mean rate of vector change per month.
Vector – vector analysis summary (mean and SD of IRC , SIRC , EV , CR and ER by preop MRC categories)
Vector – EM (mean and SD by preop MRC categories)
Vector – EA (mean and SD by preop MRC categories)
Keratometric analysis x
Average K (defined as (flat+steep)/2) - (N, mean, SD, min, max) Stability of Average K - two sets of tables (consecutive/consistent cohorts)
Average K change between visits (n, %, 95% Cl of eyes of within ±0.5D /±1.0D change)

K cylinder magnitude difference from preop - (N, mean, SD, min, max)		
Absolute K cylinder axis shift (<15 °, \geq 15°) from preop by K cylinder magnitude(0.00 D, >0 D to \leq 0.50 D, >0.50 D to \leq 1.00 D, >1.00 D to \leq 1.50D etc.) at stability time point		
HOA analysis		x
HOA overtime - (n, mean and SD) HOA paired difference – (n, mean and 95% CI around the mean)		
IOP		x
IOP over time – (N, mean, SD, min, max)		
Change in IOP(decrease>10mmHg, decrease 6-10mmHg, decrease 1 to 5mmHg, no change, increase 1 to 5mmHg, increase 6-10 mmHg and increase>10mmHg) from preop - (n, %)		
Medical findings from slit lamp examination over time (n and %)		x
Corneal clarity ratings over time (from slit lamp exam; n and %)		x
Shirmer I Tear Test		x
Test score summary(N, mean, SD, min, max at preop and at the stability time point) and change in the test score (N, mean, SD, min, max)		
OSDI Mean OSDI total score at each visit. N and % of dry eye symptoms categorized as none, mild, moderate and severe.		
NEI-RQL-42 questionnaire data Mean of the 13 scales at preop and at the stability time point. Mean paired difference will be calculated.	x	

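### Spherical aberration is planned only as an unsigned RMS, so its paired change can understate, cancel or reverse a real shift in eyes that are negative or cross zero

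*SAP*

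**What the plan says.** SAP 6.7 lists "root mean square (RMS) values for total higher order aberrations and key specific components: coma, trefoil, and spherical aberration" and fixes the diameter: "Analyses will be performed for 5 mm wavefront diameters". Means and standard deviations are reported over time. For change it says: "A paired analysis will be done for HOA change between preoperative visit and at the stability time point", and "Mean change and 95% confidence interval will be provided for each HOA".

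The HOA rows of SAP Appendix I repeat this as "HOA paired difference – (n, mean and 95% CI around the mean" and add no signed row. Protocol 20.3 is more general: "Mean iDesign aberrometry measurements (HOA) and changes in HOAs will be presented". Protocol 6.2 places the measurement among the other endpoints, as "iDesign aberrometry measurements (including higher order aberrations", with no success criterion. Neither document mentions the sign of spherical aberration.

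**The concern.** An RMS cannot be negative. Spherical aberration, taken as one coefficient, can have either sign, and a treatment can move it up or down. A paired change in RMS compares two absolute values. It answers whether the aberration became larger or smaller, but not by how much or in which direction the treatment moved the coefficient.

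The second question is a natural one here, because Protocol 7.1 says the treatment profile is calculated from the wavefront measurement. The SAP keeps direction for other outcomes: it separates under- from over-correction of MRSE (5.1), reports rises and falls in IOP separately (6.8), and analyses cylinder by both non-vector and vector methods (6.5). At stake is whether the HOA table can show a systematic shift in spherical aberration. A signed result cannot be recovered from a table of RMS means.

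**Working it through.** **Inputs.** From SAP 6.7: RMS as the metric, 5 mm diameter, paired mean change with 95% CI. The documents give no mean, SD, expected shift or power statement for any HOA, so there is no planned figure to reproduce. All µm values below are assumptions.

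**Step 1: one eye.** For a single coefficient c, RMS = √(c²) = |c|. The planned change is |post| − |pre|, and the signed change is post − pre. The size of the first can never exceed the size of the second.

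| Pre (µm) | Post (µm) | Signed change | RMS change | Effect |
|---|---|---|---|---|
| +0.05 | +0.25 | +0.20 | +0.20 | nothing lost |
| −0.05 | +0.15 | +0.20 | +0.10 | half lost |
| −0.10 | +0.10 | +0.20 | 0.00 | cancelled |
| −0.10 | +0.05 | +0.15 | −0.05 | crosses zero, direction wrong |
| −0.30 | −0.10 | +0.20 | −0.20 | fully reversed |

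**Step 2: the mean over eyes.** Let the preoperative coefficient be X ~ N(m, s), with every eye shifting by d. The folded-normal mean is

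E|X| = s·√(2/π)·exp(−m²/(2s²)) + m·[1 − 2Φ(−m/s)],

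and the expected RMS change is E|X + d| − E|X|.

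Worked case, m = 0, s = 0.10, d = +0.10:
- E|X| = 0.10 × 0.7979 = 0.0798
- E|X + d| = 0.0798 × 0.6065 + 0.10 × (1 − 2 × 0.1587) = 0.0484 + 0.0683 = 0.1167
- RMS change = 0.1167 − 0.0798 = 0.0369, or 37% of the true +0.10.

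Mean RMS change as a share of a true shift d = +0.10 µm:

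| Preoperative mean m (µm) | s = 0.10: eyes negative | s = 0.10: share shown | s = 0.05: eyes negative | s = 0.05: share shown |
|---|---|---|---|---|
| −0.10 | 84% | −37% | 98% | −61% |
| −0.05 | 69% | 0% | 84% | 0% |
| 0 | 50% | 37% | 50% | 61% |
| +0.05 | 31% | 66% | 16% | 92% |
| +0.10 | 16% | 85% | 2% | 99% |
| +0.20 | 2% | 98% | 0% | 100% |

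The share also depends on d. At m = 0 and s = 0.10 it is 20% for d = +0.05 and 61% for d = +0.20.

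**Step 3: a downward shift.** With m = +0.05 and d = −0.10 the postoperative mean is −0.05. By symmetry E|X| is unchanged, so the mean RMS change is exactly zero. A mainly positive preoperative sample therefore does not by itself remove the problem.

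**Step 4: the signed coefficient.** Its mean paired change equals d in every scenario above. It has its own blind spot. If half the eyes go from 0 to +0.10 and half from 0 to −0.10, the mean signed change is 0 while the mean RMS change is +0.10.

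**The case against.** **The estimand is not stated.** Neither document says that the target is the signed shift. An eye that goes from −0.10 to +0.10 µm does have an unchanged amount of spherical aberration, and change in RMS estimates change in magnitude without error. This stands: the RMS analysis is legitimate and should remain.

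**The text is not exclusive.** SAP 6.7 says "Analyses of higher order aberrations (HOA) from iDesign aberrometry measurements will include" RMS values, and the paired sentence speaks of HOA change, not of RMS change. That leaves room for a signed analysis but does not plan one, and RMS is the natural reading of the paired analysis.

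**RMS drops direction for coma and trefoil too.** True: coma that rotates by 180° shows no RMS change. The difference is practical. Spherical aberration, as one coefficient, has a simple signed form that needs one extra row.

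**The sizes are assumed, and so is the single coefficient.** Both true. The SAP does not say which terms enter the spherical aberration RMS. If several are pooled, the absolute value is only an approximation, but sign is still lost.

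**The signed values can be produced later from stored data.** Also true, and it limits the harm. A pre-specified row is still better than one chosen after the results are seen.

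**Conclusion.** SAP 6.7 specifies spherical aberration only as a magnitude, and the paired mean change and its interval, read naturally, rest on that magnitude. Taken as a single signed coefficient, the RMS change reproduces the signed shift where eyes stay positive. It falls short of the shift where eyes cross zero, and reverses it where both values are negative.

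A reader might infer that the planned analysis is generally biased toward no change, or that its interval is centred on the wrong quantity. The documents do not support this. Nothing is lost in eyes that stay positive, the error can be a reversal and not only a shrinkage, and the interval is correct for change in magnitude.

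The size in this trial cannot be fixed, because the preoperative distribution and the expected shift are not given. Under the assumed normal distributions with a uniform +0.10 µm shift, the loss runs from almost none to total, and on to a reversal.

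This is a minor point. HOA carries no success criterion or power statement, and the primary endpoints and sample size are untouched.

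**What to change.** In SAP 6.7 and the HOA rows of Appendix I, keep the RMS analyses for total HOA, coma, trefoil and spherical aberration. Add the signed spherical aberration coefficient at the same 5 mm diameter: mean and SD over time, and paired mean change from preoperative to the stability time point with 95% CI. State which coefficient is meant.

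Report both forms. Replacing the RMS would have a cost, because a signed mean can hide opposite shifts just as an RMS can hide a change of sign.

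The change is one sentence and one table row. Aberrometry is already part of the iDesign measurement, taken preoperatively and at each visit from 1 to 12 months (Protocol Appendix A), so no new testing is needed.

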6.8 INTRAOCULAR PRESSURE (IOP)

Summary statistics (mean, standard deviation, minimum and maximum) will be reported over time for IOP. The frequency and proportion of eyes with changes in IOP from preoperative visit (decrease >10 mmHg, decrease 6 to 10 mmHg, decrease 1 to 5 mmHg, no change, increase 1 to 5 mmHg, increase 6 to 10 mmHg, increase >10 mmHg) will be presented over time.

6.9 ANTERIOR SEGMENT EVALUATION

Rates of postoperative medical findings noted from the biomicrocopy slit lamp examination, including degree of corneal clarity, will be tabulated with the frequency and proportion of eyes with findings reported over time.

6.10 NEI-RQL-42 QUESTIONNAIRE DATA

Analysis of the National Eye Institute Refractive Quality of Life *(NEI-RQL-42)* patient-reported outcomes instrument will be done according to the NEI-RQL-42 User's Manual, Version 1.0 (see Appendix IV). Items that are left blank (missing data) are not taken into account when calculating the scale scores. Scores represent the average for all items in the scale that the respondent answered. For items 36b to 42b, each has four response levels, but is expanded to five levels using items 36a to 42a, respectively. If 'a'=2, then 'b' should be left blank. If there is a discrepancy between 'a' and 'b', ignore the response to 'a' and go with the response to 'b'. The 13 sub-scales of the NEI-RQL-42 will be analyzed and reported over time. The mean of each of the sub-scales will be calculated at preoperative visit and at the time point of refractive stability. The paired difference of each of the sub-scales between preoperative visit and the time point of refractive stability will be reported.

6.11 OSDI QUESTIONNAIRE

The OSDI mean total score will be calculated and dry eye symptoms categorized as normal (0-12 points), mild (13-22 points), moderate (23-32 points) and severe (33-100 points) will be reported preoperatively and postoperatively over time.

6.12 OCULAR VISUAL SYMPTOMS

The frequency and proportion of eyes with spontaneously reported ocular visual symptoms (nondirected) will be presented. Additionally, the frequency and proportion of eyes with different levels of severity of specific visual symptoms based on the Patient Reported Visual Symptom Questionnaire (PRVSQ PRO) will be reported. No imputations for missing values should be used for PRVSQ-LASIK/PRK item responses; that is, any item with a missing response will be maintained as a missing value for analysis. However, any patient that provides a written-in limitation to question F, but fails to explicitly answer "Yes" to the item will be considered as having provided a "Yes" response to question F. To conservatively classify severe visual symptoms, any patient that reports an extreme level of bother (i.e., "Extremely bothered" to question E) and limitations due to that symptom (i.e., "Yes" to question F) will be considered having a severe symptom, regardless of missing responses on any other item. Note that results from the PRSVQ questionnaires completed following the 3-month study visit will be used for reliability validation purposes for the PRSVQ only and will not be analyzed in this study or used for AE reporting).

6.13 COMPLICATIONS/ADVERSE EVENTS/NON-REFRACTIVE RETREATMENT PROCEDURE

The frequency and proportion of eyes with specific complications and adverse events following the ANSI Guidance Document for Corneal Reshaping, Z80.11-2012) will be presented over time. A listing of all serious and/or device-related adverse events will also be provided. Additionally, non-refractive retreatment procedures will be tabulated and summarized.

6.14 SCHIRMER I TEAR TEST (WITH ANESTHETIC)

The mean scores of Schirmer I Tear Test at preoperative visit and at the stability time point will be presented. The mean paired change in Schirmer I Tear Test score will be reported.

6.15 EXPLORATORY SATISFACTION QUESTIONNAIRES

The frequency and proportion of patients with satisfaction about the study procedure from the nonvalidated questionnaires designed to collect patient satisfaction data prior to and following refractive corneal surgery will be summarized.

For comparisons across categories, a Mantel-Haenszel chi-square test for ordinal data and a Cochran-Mantel-Haenszel test for non-ordinal data will be used to compare the observed percentages across categories. Additionally, the results for each category will be compared to the target criterion for each study endpoint using chi-square goodness-of-fit test. All statistical tests and p-values will be reported as 2-sided and a significance level of 0.15 will be used to assess homogeneity of the primary safety and effectiveness endpoints for baseline and demographic variables.

Statistical significant factors will be further investigated.

8 INTERIM ANALYSES

Up to four interim analyses may be conducted to determine the point of refractive stability when 90% of treated subjects have reached the 3, 6, 9 and 12 month visits, respectively. These analyses will only include refractive stability criteria evaluation.

9 SAMPLE SIZE CALCULATIONS

Per ANSI Z80.11-2012, Annex E, the sample size calculation is to be based on the probability of observing an adverse event at a rate greater than or equal to the expected rate but less than or equal to an acceptable target. This study will be powered to detect the percentage of eyes losing 2 or more lines of BSCVA at 3 months. In the approved indication for the original STAR S4 IR System Myopia clinical study (PMA P930016-S016, approved 05/23/03), the percentage of eyes losing 2 or more lines of BSCVA at 3 months was 0.3% (1/318, 95% exact CI (0.00%, 1.7%)). The target rate will be chosen to assure that the proposed study will be able to detect at least the upper limit of the exact 95% confidence interval.

The hypothesis is

$$H_{o}: p_{trt} \leq p_{target}$$

$$H_1$$
: $p_{trt} > p_{target}$

where

 p_{trt} = Estimate of the percentage of eyes losing 2 or more lines of BSCVA at 3 months using the STAR S4 IR and iDesign System

18NOV2015/3.0

p_{target} = Expected percentage of eyes losing 2 or more lines of BSCVA at 3 months per previously approved PMA P930016-S016

Using the binomial distribution with an alpha of 0.05, 80% power and a sample size of n=300 eyes, a rate of at least 1% can be detected. Therefore, a sample size of 300 evaluable eyes at the time point of stability is required.

CONTRAST SENSITIVITY SUBSTUDY SAMPLE SIZE

The sample size calculation for the substudy is based on ANSI guidance (ANSI Z80.11) using noninferiority approach. With a sample size is 65, a paired t-test with a 0.05 one-sided significance level will have over 90% power to detect the paired difference mean contrast sensitivity is no less than 0.15 below zero when the expected mean difference is 0, assuming the non-inferiority margin equals 0.15 and the standard deviation of the difference is 0.40.

